8.9.2 Pharmacodynamics and Mechanism of Action

The PD effects of BMS-986165 will be assessed based on markers in blood and urine, which will be collected at the timepoints shown in [Section 1.3](#) and in [Table 7](#). Serum and plasma samples will be collected and analyzed for markers of tissue damage and regeneration, such as markers of inflammatory damage to collagen. Samples will be collected predose except for the FP visit. Samples can also be collected at any time for the Day 2 or 3 sample, which will be collected for a subset of subjects for blood ribonucleic acid (RNA) and inflammatory markers (this will be performed in a home visit or other means to avoid requiring subjects to return to the site).

Lupus is an inflammatory/autoimmune disorder that results in damage to many different tissues. It is characterized by elevated expression of the Type I IFN pathway. To assess the effect of BMS-986165 on the IFN pathway, blood samples for RNA will be collected to assess the expression of IRGs and other genes.

Patients with lupus typically have decreases in complement proteins, C3 and C4, and circulating lymphocytes. These will be assessed for evidence of PD activity. Anti-dsDNA will also be assessed for PD changes in serum and plasma.

BMS-986165 is expected to inhibit the actions of IL-12 and IL-23. This should result in alterations to T-helper cell phenotypes. In addition, B-cell populations are dysregulated in lupus, with increases in activated phenotypes. Blood will be collected for lymphocyte profiling including assessments of T-helper subpopulations, activated and memory T-cell subpopulations, B-cell populations, and dendritic cell populations. These populations will be enumerated in samples from a subset of subjects in the USA. In addition, the effects of BMS-986165 on IL-12- and IL-23-regulated genes and proteins will also be assessed.

Corticosteroid treatment is common in lupus; however, the effectiveness of this treatment varies in different patients. Thus, a broad range of doses are used across patient populations and even over time within individual patients. This treatment can confound the interpretation of investigational clinical trials. To address this issue, the biological effect of CS use will be assessed by measuring a gene signature of CS exposure.

Lupus patients have characteristic alterations in blood cell populations and activation status. Blood samples will be collected to assess the numbers and activation status of lymphocyte and leucocyte cell subsets.

[REDACTED]

[REDACTED]

[REDACTED]

[REDACTED]

9 STATISTICAL CONSIDERATIONS

9.1 Sample Size Determination

Approximately 360 subjects will be randomized into 1 of 4 treatment arms in a 1:1:1:1 ratio, resulting in around 90 subjects per arm. [REDACTED]

[REDACTED]

[REDACTED] With a sample size of 90 subjects per arm, there will be at least 84% power to detect a treatment difference of 20% in SRI(4) response rates between the BID BMS-986165 treatment arms and placebo [REDACTED]

9.2 Populations for Analyses

The following populations are defined for analysis purposes:

| Population | Description |
|---------------------------------|--|
| Enrolled | All subjects who sign informed consent. |
| Randomized | All subjects who are randomized to a treatment. Subjects will be grouped according to the treatment to which they are randomized according to IRT at the start of the TP. |
| Modified intent-to-treat (mITT) | All subjects who are randomized and have received at least 1 dose of study treatment. Subjects will be grouped according to the treatment to which they are randomized within the IRT at the start of the TP. The mITT population will be the same as the Randomized population if all randomized subjects receive at least 1 dose of study treatment. |
| Biomarker | All subjects who receive at least 1 dose of study treatment and have at least 1 posttreatment biomarker measurement. |
| Pharmacokinetic | All subjects who receive at least 1 dose of BMS-986165 and have any available concentration-time data. |
| As-treated | All subjects who receive at least 1 dose of double-blind study treatment, analyzed according to the treatment actually received, regardless of assigned treatment. |
| Per Protocol Set (PPS) | All subjects who are compliant with study treatment (compliance criteria will be defined in the SAP) and who do not have any relevant protocol deviations that may impact the primary efficacy endpoint assessments. The PPS will be a supportive efficacy analysis population. |

9.3 Statistical Analyses

The SAP will be developed and finalized before database lock for the primary efficacy analysis and will provide detailed specifications of the analysis of all efficacy endpoints and safety, and it will also describe the selection of subjects to be included in the analyses and procedures for

accounting for missing data. This section provides a summary of planned statistical analyses of the primary and secondary endpoints.

9.3.1 Efficacy Analysis

9.3.1.1 Endpoints

Primary Efficacy Endpoint

[figure not shown]
The primary efficacy endpoint is:

- Proportion of subjects who meet SRI(4) response at Week 32 (SRI response is defined in [Section 8.1](#))

Secondary Efficacy Endpoints

Secondary efficacy endpoints are as follows:

- Proportion of subjects who meet SRI(4) response at Week 48
- Proportion of subjects who achieve BICLA response at Week 48, where BICLA response is defined as follows:
 - Improvement in all organ systems with activity graded as BILAG-2004 A or B at baseline
 - No new organ system with activity graded as BILAG A; no more than 1 new organ system with activity graded as BILAG B
 - No increase from baseline in SLEDAI-2K (≤ 0 points for change from baseline score)
 - No increase $\geq 10\%$ in the Physician's Global Assessment of Disease Activity on a 3-point VAS
 - No discontinuation of IP or use of restricted medications beyond the protocol allowed threshold before assessment
- Proportion of subjects who achieve LLDAS at Week 48
- Proportion of subjects with a CLASI activity score ≥ 10 at baseline who achieve a CLASI response, defined as a decrease of $\geq 50\%$ from baseline CLASI activity score at Week 48
- Change from baseline in the 40-joint count for tender, swollen, and tender + swollen joints at Week 48

9.3.1.2 Nonresponders

Subjects will be considered nonresponders in the TP for the responder-type efficacy endpoints (ie, BICLA and SRI) in the primary and secondary analyses at weeks 32 and 48, respectively, if they meet any of the following criteria:

- Requires CS dose > 7.5 mg/day prednisone or equivalent after Week 20
- Requires CS rescue therapy beginning after the Week 8 visit
- Requires more than 1 burst of CS rescue therapy
- Requires dose increase in background immunosuppressant or antimalarial medication
- Requires treatment with medications prohibited by the protocol ([Section 6.7.1](#) and [APPENDIX 7](#))
- Discontinues treatment before the assessment timepoint or has a missing value for the particular endpoint

Nonresponder definitions for other time points will be provided in the SAP.

9.3.1.3 Analysis Methodology

[figure not shown]
General Summaries

Summaries will be provided for the following efficacy variables by each visit for which the variable is collected, in addition to the above endpoints:

- Proportion of subjects who:

- Meet SRI(4) response criteria
- Meet BICLA response criteria
- Meet LLDAS response criteria
- Have a CLASI activity score ≥ 10 at baseline who achieve a CLASI response, defined as a decrease of $\geq 50\%$ from baseline CLASI activity score
- Are receiving a daily CS dose ≤ 7.5 mg/day prednisone (or equivalent) in those receiving CS at baseline
- Change from baseline in:
 - BILAG-2004 score
 - SLEDAI-2K score
 - Joint counts for tender, swollen, and tender + swollen joints
 - Physician’s Global Assessment of Disease Activity

- CLASI activity score in subjects with a CLASI activity score ≥ 10 at baseline

Statistical Methodology

Efficacy analyses will be performed using the population of randomized subjects.

| Endpoint | Statistical Analysis Methods |
|----------|--|
| Primary | 
The primary endpoint, the proportion of subjects who meet the response criteria for SRI(4) at Week 32, will be analyzed using logistic regression with covariate for the randomization stratum to compare the response rates between each treatment group and placebo. The odds ratio (odds for active treatment /odds for placebo) and the corresponding 2-sided 95% confidence interval (CI) will be provided from the logistic regression model. Additionally, a sensitivity analysis will be conducted using a Cochran-Mantel-Haenszel (CMH) chi-square test stratified by randomization stratum; or alternatively a chi-square test if a CMH test cannot be performed. Differences in response rates and corresponding 2-sided 95% CI will be provided along with the point estimates and corresponding 95% CI for each group using a binomial model.
 
The above analyses will be conducted for the mITT population. The primary efficacy analysis will be performed after all subjects have completed Week 48 efficacy assessments (or discontinued).
 |

[figure not shown]

| Endpoint | Statistical Analysis Methods |
|----------------------|--|
| Secondary [REDACTED] | 
Similar analyses will be performed as for the primary efficacy analyses for the proportion-type secondary [REDACTED] efficacy endpoints to compare differences between the active treatment groups and placebo.
 
The response rates over time will be analyzed using a repeated measure model when applicable.
 
Repeated continuous measures will be analyzed using a mixed effect model with treatment, visit, treatment-by-visit interaction, and randomization stratum as the fixed effects and changes from baseline within each subject as the repeated measurements. The baseline value will be added into the model as a covariate. Based on the mixed effect model, the point estimate, and 95% CI will be calculated for the difference between each active treatment group and the placebo group at each specified visit.
 
All analyses will be conducted for the mITT population. The handling of missing values will be described in the SAP.
 |

[REDACTED]

Additionally, subgroup analyses to be performed will be described in the SAP.

[REDACTED]

9.3.2 Safety Analyses

Safety analyses will be performed using the As-treated population. The primary safety endpoint is a secondary endpoint of the study. For analysis, all recorded AEs will be listed and tabulated by system organ class, preferred term, and treatment. Vital signs and clinical laboratory test results will be listed and summarized by treatment. ECG readings will be evaluated by the investigator and abnormalities, if present, will be summarized and listed.

9.3.3 Other Analyses

9.3.3.1 Pharmacokinetics

PK evaluation is a secondary endpoint. Plasma concentration values will be summarized by dose and study day using descriptive statistics. If warranted, analysis of PK and exposure-response relationships of BMS-986165 will be conducted using a population approach as appropriate and reported separately from the clinical study report.

9.3.3.2 Pharmacodynamics

Pharmacodynamic evaluation is a secondary endpoint. Selected PD endpoints such as IRG expression, C3, C4, and anti-dsDNA will be summarized by treatment and timepoint, and their corresponding changes and percent change from baseline will be calculated and summarized. Change from baseline in lymphocyte count, serum or plasma proteins, genome-wide RNA expression, lymphocyte subsets and activation status, etc, will be summarized by time. Baseline values will be defined as the last measurement before the first dose.

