| 
Pharmacodynamics
 
 To assess the effect of BMS-986165 on PD markers (Section 8.9.2) | 
 Change in mean and median interferon-regulated gene (IRG) expression levels compared to baseline over time and at Week 32 Change in mean complement (C3, C4) and anti-double-stranded DNA (dsDNA) levels compared to baseline over time and at Week 32 Assess the effect of BMS-986165 on measures of global SLE clinical response in subjects based on IRG status (ie, high versus low IRG signature) at Week 32 |

Table 4: Objectives and Endpoints

| Objectives | Endpoints |
|------------|-----------|
| | |
| | |

Table 4: Objectives and Endpoints

| Objectives | Endpoints |
|------------|-----------|
| | |

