13.0 Biomarker Analysis

Summaries will be provided for the biomarker analysis population. Summaries include mean, SD, median, IQR, range, change from baseline and percent change from baseline. Summaries for the following biomarkers will be provided for treatment arms as well as for baseline IFN status (IFN-high and IFN-low) under each arm at each analysis visit. IFN-high vs. IFN-low will be designated based on IFN evaluation of samples collected during the screening period. Demographic information of subjects for each IFN status will be provided.

- aggregated genes (IRGs [redacted])

- clinical markers: C3, C4, Coomb's test, anti-dsDN [redacted]

% Change of individual IRGs will be derived as follows:

- The log₂ Fold Change of each gene of each subject = [normalized log₂ value at time point]-[normalized log₂ value at Day 1 predose]
- % Change from Baseline of each gene at a time point = $[2^{(\log_2 \text{ Fold Change})} - 1] \times 100$

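### For IRG, C3, C4 and anti-dsDNA the visible plan gives only per-arm descriptive summaries, with no planned difference from placebo, no confidence interval, and no baseline or stratum covariate

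*Protocol*

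**What the plan says.** Protocol section 3 (Table 4) gives the PD objective as "To assess the effect of BMS-986165 on PD markers". Two of the PD endpoints under it concern marker levels: "Change in mean and median interferon-regulated gene (IRG) expression levels compared to baseline over time and at Week 32" and "Change in mean complement (C3, C4) and anti-double-stranded DNA (dsDNA) levels compared to baseline over time and at Week 32". A third concerns clinical response by IRG status.

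Protocol 9.3.3.2 states "Pharmacodynamic evaluation is a secondary endpoint" and then gives the method: "Selected PD endpoints such as IRG expression, C3, C4, and anti-dsDNA will be summarized by treatment and timepoint", together with changes and percent changes from baseline.

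SAP 13.0 fills this in. "Summaries include mean, SD, median, IQR, range, change from baseline and percent change from baseline", and these "will be provided for treatment arms as well as for baseline IFN status (IFN-high and IFN-low) under each arm at each analysis visit".

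Elsewhere the protocol has a model for data of this shape. Section 9.3.1.3, under Efficacy Analysis, says "Repeated continuous measures will be analyzed using a mixed effect model with treatment, visit, treatment-by-visit interaction, and randomization stratum as the fixed effects". The baseline value is a covariate, and the output is a difference from placebo with a 95% CI at each specified visit. In the visible SAP, the detailed version of that model (11.7.2.5) is applied to the three joint-count endpoints.

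**The concern.** An objective about the effect of a drug, in a randomized placebo-controlled trial, calls for a contrast with placebo and a statement of its uncertainty. The planned tables give each arm's mean, spread and change separately. A reader who wants to know how far a regimen moves the interferon signature or complement beyond placebo must subtract one column from another, with no planned interval.

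Two pieces of information that the trial collects are also left unused. Change from baseline is calculated, but the baseline value does not enter as a covariate. The randomization stratum does not enter at all.

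What is at stake is the comparison of PD activity across three regimens. Protocol 2.1 says the study is intended to learn whether the pharmacological effects go with improvement in disease activity and related biomarkers, and it also looks to exposure-response relationships for PD endpoints. Planned estimates with intervals would serve those aims better than arm summaries read side by side.

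**Working it through.** The documents give no sample size, power, SD or correlation for the PD markers, so there is no plan figure to reproduce. The check is first textual, then a short illustration of what adjustment would gain.

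**Step 1. What is planned for each kind of endpoint (visible text).**

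| Item | Joint counts (Protocol 9.3.1.3, SAP 11.7.2.5) | IRG, C3, C4, anti-dsDNA (Protocol 9.3.3.2, SAP 13.0) |
|---|---|---|
| Per-arm summaries | yes | yes |
| Active minus placebo | yes | not planned |
| 95% CI for that difference | yes | not planned |
| Baseline as covariate | yes | no (only change and percent change) |
| Randomization stratum | yes | no |

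The visible list of continuous endpoints in SAP 11.7 contains joint counts and the global BILAG score, and no PD marker. Parts of Protocol 9.3.1.3 and of SAP 11.7 and 13.0 are blacked out or blank. In SAP 13.0 the visible redactions fall in the list of markers, not in the sentence that names the statistics.

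**Step 2. Could the data support the contrast?** Complement and anti-dsDNA are scheduled at every joint-count visit in the treatment period, and IRG blood is drawn predose on the same study days. A baseline value is defined in Protocol 9.3.3.2. For individual IRGs, SAP 13.0 already works with the log2 difference from Day 1 predose.

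**Step 3. Gain from adjusting for baseline.**

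Inputs:
- about 90 subjects per arm (Protocol 9.1)
- marker SD set to 1 at baseline and follow-up (assumed equal)
- correlation r between baseline and follow-up (assumed; not in the documents)

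Formulas:
- variance of a change score: 2(1 − r)
- variance after baseline adjustment: 1 − r²
- ratio: (1 − r²) / [2(1 − r)] = (1 + r)/2
- 95% CI half-width for active minus placebo: 1.96 × SD × √(2/90), where √(2/90) = 0.149

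| r | Variance ratio | Half-width, change score | Half-width, adjusted |
|---|---|---|---|
| 0.5 | 0.75 | 1.96 × 1.000 × 0.149 = 0.292 SD | 1.96 × 0.866 × 0.149 = 0.253 SD |
| 0.6 | 0.80 | 0.261 SD | 0.234 SD |
| 0.7 | 0.85 | 0.226 SD | 0.209 SD |
| 0.8 | 0.90 | 1.96 × 0.632 × 0.149 = 0.185 SD | 1.96 × 0.600 × 0.149 = 0.175 SD |

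The variance is 10% to 25% lower. Since √0.90 = 0.95 and √0.75 = 0.87, the interval is 5% to 13% narrower. With only 60 per arm sampled and r = 0.5, the adjusted half-width would be 0.310 SD. Any further gain from the strata is not counted.

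**Step 4. If the variances are not equal.** Suppression of IRG could change the spread at follow-up. With baseline SD a and follow-up SD b, the change-score variance minus the adjusted variance is a² + b² − 2rab − b²(1 − r²) = (a − rb)², which cannot be negative. The size of the gain therefore depends on the equal-variance assumption, but in large samples adjustment does not lose precision.

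**The case against.** The strongest reply is that the plan delivers the endpoints as they are worded. Table 4 defines the marker endpoints as change compared with baseline, and the summaries give that. This stands: the plan does not contradict itself. Only the broader objective, an effect of the drug, asks for more.

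Second, Protocol 9.3.3.2 calls PD secondary, so the mixed model for secondary endpoints in 9.3.1.3 might be meant to apply. Its place under Efficacy Analysis and the descriptive wording of SAP 13.0 tell against that, though redactions prevent certainty.

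Third, Protocol 9.3.3.1 allows exposure-response modelling. It is conditional and does not name these markers, so it softens the gap without closing it.

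There are also stronger readings that a reader might infer and that the documents do not support:

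- *That the drug's effect on the markers cannot be recovered.* Placebo is summarized beside each regimen with mean, SD and change. A crude randomized difference follows from the tables, and an approximate interval too if n is shown.
- *That no PD secondary endpoint gets a comparison with placebo.* The third one, response by IRG status, is partly served by SAP 11.7.4: SRI(4) at Week 32 by interferon status, with an unadjusted difference and Newcombe limits.
- *That steroid tapering and regression to the mean make the results misleading.* All arms share the same taper rules and entry criteria, so these influences are largely common to placebo. They mislead mainly a reader who ignores the placebo column.
- *That drop-out biases the comparison.* The documents give no drop-out figures for these markers, and an error common to the arms cancels in the difference.

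**Conclusion.** The point holds for four markers, on the visible text. IRG, C3, C4 and anti-dsDNA have no planned active-minus-placebo estimate, no interval, and no baseline or stratum covariate, although the objective is the drug's effect on PD markers.

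The main gain from correcting this is a prespecified estimate with its uncertainty. The gain in precision is modest and rests on an assumed correlation and equal variances. At r = 0.8 the interval narrows by only about 5%.

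The SRI(4) primary analysis and the Week 48 endpoints in the multiplicity-controlled hierarchy are untouched. This is an optional, inexpensive improvement.

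**What to change.** In SAP 13.0, with matching wording in Protocol 9.3.3.2, add for each of the four markers a mixed model on change from baseline. Use a log scale for IRG and anti-dsDNA. The terms are treatment, visit, treatment-by-visit, randomization stratum (as defined in SAP 6.5) and baseline value. Report each regimen's difference from placebo with a 95% CI at Week 32 and over time. Label these as nominal estimates outside the multiplicity procedure. Keep the descriptive tables, including the split by interferon status.

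Two details need stating, because the joint-count model cannot simply be copied:

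- *Which scheduled predose visits enter.* The joint-count model uses only Weeks 24, 32 and 48, while IRG and complement are also sampled at Week 2, and IRG has post-dose samples on Day 85.
- *Whether the set-to-missing rule applies.* SAP 11.7.2.5 discards observed joint counts at visits that meet the non-responder criteria. Whether PD values are treated the same way changes what is being estimated. The model will in either case rely on a missing-at-random assumption.

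The cost is the added wording and one further model per marker. The downside is a few more tables whose results are not controlled for multiplicity.

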9.3.4 Interim Analyses

One interim analysis may be performed after at least 50% of subjects have achieved the Week 32 primary endpoint to aid in planning for subsequent clinical development. Details and timing of the interim analysis will be described in the SAP. Results will be reviewed by an unblinded Sponsor team independent from the blinded study team. The unblinded team will provide recommendations to the blinded study team as appropriate. The study team responsible for managing the study, including medical monitors, will remain blinded. The SAP will further describe any potential interim analyses.

[figure not shown]
9.3.5 Analysis and Reporting

The final database lock will occur once all randomized subjects have completed 48 weeks of double-blind treatment (or have discontinued) and the 4-week safety follow-up for those who have not enrolled into the LTE study IM011074. Details of these efficacy and safety analyses will be described in the SAP.

11 APPENDICES

APPENDIX 1 STUDY GOVERNANCE CONSIDERATIONS

The term ‘Participant’ is used in the protocol to refer to a person who has consented to participate in the clinical research study. The term ‘Subject’ used in the eCRF is intended to refer to a person (Participant) who has consented to participate in the clinical research study.

REGULATORY AND ETHICAL CONSIDERATIONS

GOOD CLINICAL PRACTICE

This study will be conducted in accordance with:

- Good Clinical Practice (GCP)
- as defined by the International Council for Harmonisation (ICH)
- in accordance with the ethical principles underlying European Union Directive 2001/20/EC
- United States (US) Code of Federal Regulations, Title 21, Part 50 (21CFR50)
- applicable local requirements

The study will be conducted in compliance with the protocol. The protocol and any amendments and the participant informed consent will receive approval/favorable opinion by Institutional Review Board/Independent Ethics Committee (IRB/IEC), and regulatory authorities according to applicable local regulations prior to initiation of the study.

All potential serious breaches must be reported to Sponsor or designee immediately. A serious breach is a breach of the conditions and principles of GCP in connection with the study or the protocol, which is likely to affect, to a significant degree, the safety or physical or mental integrity of the subjects of the study or the scientific value of the study.

Personnel involved in conducting this study will be qualified by education, training, and experience to perform their respective tasks.

This study will not use the services of study personnel where sanctions have been invoked or where there has been scientific misconduct or fraud (eg, loss of medical licensure, debarment).

INSTITUTIONAL REVIEW BOARD/INDEPENDENT ETHICS COMMITTEE

Before study initiation, the investigator must have written and dated approval/favorable opinion from the IRB/IEC for the protocol, consent form, participant recruitment materials (eg, advertisements), and any other written information to be provided to subjects. The investigator or BMS should also provide the IRB/IEC with a copy of the Investigator Brochure or product labeling information to be provided to subjects and any updates.

The investigator, Sponsor or designee should provide the IRB/IEC with reports, updates and other information (eg, expedited safety reports, amendments, and administrative letters) according to regulatory requirements or institution procedures.

COMPLIANCE WITH THE PROTOCOL AND PROTOCOL REVISIONS

The investigator should not implement any deviation or change to the protocol without prior review and documented approval/favorable opinion of an amendment from the IRB/IEC (and if

applicable, also by local health authority) except where necessary to eliminate an immediate hazard(s) to study subjects.

If a deviation or change to a protocol is implemented to eliminate an immediate hazard(s) prior to obtaining relevant approval/favorable opinion(s) the deviation or change will be submitted, as soon as possible to:

- IRB/IEC
- Regulatory Authority(ies), if applicable by local regulations (per national requirements)

Documentation of approval/favorable opinion signed by the chairperson or designee of the IRB(s)/IEC(s) and if applicable, also by local health authority must be sent to BMS.

If an amendment substantially alters the study design or increases the potential risk to the participant: (1) the consent form must be revised and submitted to the IRB(s)/IEC(s) for review and approval/favorable opinion; (2) the revised form must be used to obtain consent from subjects currently enrolled in the study if they are affected by the amendment; and (3) the new form must be used to obtain consent from new subjects prior to enrollment.

If the revision is done via an administrative letter, investigators must inform their IRB(s)/IEC(s).

FINANCIAL DISCLOSURE

Investigators and sub-investigators will provide the Sponsor with sufficient, accurate financial information in accordance with local regulations to allow the Sponsor to submit complete and accurate financial certification or disclosure statements to the appropriate health authorities. Investigators are responsible for providing information on financial interests during the course of the study and for 1 year after completion of the study.

INFORMED CONSENT PROCESS

Investigators must ensure that subjects are clearly and fully informed about the purpose, potential risks, and other critical issues regarding clinical studies in which they volunteer to participate.

In situations where consent cannot be given to subjects, their legally acceptable representatives (as per country guidelines) are clearly and fully informed about the purpose, potential risks, and other critical issues regarding clinical studies in which the participant volunteers to participate.

Sponsor or designee will provide the investigator with an appropriate (ie, global or local) sample informed consent form (ICF) which will include all elements required by ICH, GCP, and applicable regulatory requirements. The sample ICF will adhere to the ethical principles that have their origin in the Declaration of Helsinki.

Investigators must:

- Provide a copy of the ICF and written information about the study in the language in which the participant is most proficient prior to clinical study participation. The language must be nontechnical and easily understood.
- Allow time necessary for participant or participant's legally acceptable representative to inquire about the details of the study.

- Obtain an ICF signed and personally dated by the participant or the participant's legally acceptable representative and by the person who conducted the informed consent discussion.
- Obtain the IRB/IEC's written approval/favorable opinion of the written ICF and any other information to be provided to the subjects prior to the beginning of the study, and after any revisions are completed for new information.

If informed consent is initially given by a participant's legally acceptable representative or legal guardian, and the participant subsequently becomes capable of making and communicating his or her informed consent during the study, consent must additionally be obtained from the participant.

Revise the ICF whenever important new information becomes available that is relevant to the participant's consent. The investigator, or a person designated by the investigator, should fully inform the participant or the participant's legally acceptable representative or legal guardian, of all pertinent aspects of the study and of any new information relevant to the participant's willingness to continue participation in the study. This communication should be documented.

The confidentiality of records that could identify subjects must be protected, respecting the privacy and confidentiality rules applicable to regulatory requirements, the participants' signed ICF and, in the US, the participants' signed Health Insurance Portability and Accountability Act (HIPAA) Authorization.

The consent form must also include a statement that BMS and regulatory authorities have direct access to participant records.

Subjects unable to give their written consent (eg, those with stroke or severe dementia) may only be enrolled in the study with the consent of a legally acceptable representative. The participant must also be informed about the nature of the study to the extent compatible with his or her understanding, and should this participant become capable, he or she should personally sign and date the consent form as soon as possible. The explicit wish of a participant who is unable to give his or her written consent, but who is capable of forming an opinion and assessing information to refuse participation in, or to be withdrawn from, the clinical study at any time should be considered by the investigator.

The rights, safety, and well-being of the study participants are the most important considerations and should prevail over interests of science and society.

SOURCE DOCUMENTS

The investigator is responsible for ensuring that the source data are accurate, legible, contemporaneous, original, and attributable, whether the data are hand-written on paper or entered electronically. If source data are created (first entered), modified, maintained, archived, retrieved, or transmitted electronically via computerized systems (and/or any other kind of electronic devices) as part of regulated clinical trial activities, such systems must be compliant with all applicable laws and regulations governing use of electronic records and/or electronic signatures. Such systems may include, but are not limited to, electronic medical/health records (EMRs/EHRs), adverse event tracking/reporting, protocol-required assessments, and/or drug accountability records).

When paper records from such systems are used in place of electronic format to perform regulated activities, such paper records should be certified copies. A certified copy consists of a copy of original information that has been verified, as indicated by a dated signature, as an exact copy having all of the same attributes and information as the original.

STUDY TREATMENT RECORDS

Records for study treatments (whether supplied by BMS, its vendors, or the site) must substantiate study treatment integrity and traceability from receipt, preparation, administration, and through destruction or return. Records must be made available for review at the request of BMS/designee or a Health Authority.

| If | Then |
|--|--|
| Supplied by BMS (or its vendors): | 
Records or logs must comply with applicable regulations and guidelines and should include:
 
 • amount received and placed in storage area • amount currently in storage area • label identification number or batch number • amount dispensed to and returned by each participant, including unique participant identifiers • amount transferred to another area/site for dispensing or storage • nonstudy disposition (eg, lost, wasted) • amount destroyed at study site, if applicable • amount returned to BMS • retain samples for bioavailability/bioequivalence, if applicable • dates and initials of person responsible for Investigational Product dispensing/accountability, as per the Delegation of Authority Form. |
| Sourced by site, and not supplied by BMS or its vendors (examples include investigational product sourced from the site stock or commercial supply, or a specialty pharmacy) | 
The investigator or designee accepts responsibility for documenting traceability and study treatment integrity in accordance with requirements applicable under law and the standard operating procedures of the sourcing pharmacy.
 
These records should include:
 
 • label identification number or batch number • amount dispensed to and returned by each participant, including unique participant identifiers • dates and initials of person responsible for Investigational Product dispensing/accountability, as per the Delegation of Authority Form. |

BMS or designee will provide forms to facilitate inventory control if the investigational site does not have an established system that meets these requirements.

CASE REPORT FORMS

An investigator is required to prepare and maintain adequate and accurate case histories designed to record all observations and other data pertinent to the investigation on each individual treated or entered as a control in the investigation. Data that are derived from source documents and reported on the CRF must be consistent with the source documents or the discrepancies must be explained. Additional clinical information may be collected and analyzed in an effort to enhance understanding of product safety. CRFs may be requested for adverse events (AEs) and/or laboratory abnormalities that are reported or identified during the course of the study.

For sites using the Sponsor or designee electronic data capture (EDC) tool, electronic CRFs will be prepared for all data collection fields except for fields specific to serious adverse events (SAEs) and pregnancy, which will be reported on the electronic SAE form and Pregnancy Surveillance form, respectively. If an electronic SAE form is not available, a paper SAE form can be used. Spaces may be left blank only in those circumstances permitted by study-specific CRF completion guidelines provided by Sponsor or designee.

The confidentiality of records that could identify participants must be protected, respecting the privacy and confidentiality rules in accordance with the applicable regulatory requirement(s).

The investigator will maintain a signature sheet to document signatures and initials of all persons authorized to make entries and/or corrections on CRFs.

The completed CRF and SAE/pregnancy CRFs, must be promptly reviewed, signed, and dated by the investigator or qualified physician who is a sub-investigator and who is delegated this task on the Delegation of Authority Form. Sub-investigators in Japan may not be delegated the CRF approval task. For electronic CRFs, review and approval/signature is completed electronically through the BMS EDC tool. The investigator must retain a copy of the CRFs including records of the changes and corrections.

Each individual electronically signing electronic CRFs must meet Sponsor or designee training requirements and must only access the BMS EDC tool using the unique user account provided by Sponsor or designee. User accounts are not to be shared or reassigned to other individuals

MONITORING

Sponsor or designee representatives will review data centrally to identify potential issues to determine a schedule of on-site visits for targeted review of study records.

Representatives of BMS must be allowed to visit all study site locations periodically to assess the data quality and study integrity. On site they will review study records and directly compare them with source documents, discuss the conduct of the study with the investigator, and verify that the facilities remain acceptable. Certain CRF pages and/or electronic files may serve as the source documents.

In addition, the study may be evaluated by Sponsor or designee internal auditors and government inspectors who must be allowed access to CRFs, source documents, other study files, and study facilities. BMS audit reports will be kept confidential.

The investigator must notify BMS promptly of any inspections scheduled by regulatory authorities, and promptly forward copies of inspection reports to Sponsor or designee.

RECORDS RETENTION

The investigator (or head of the study site in Japan) must retain all study records and source documents for the maximum period required by applicable regulations and guidelines, or institution procedures, or for the period specified by BMS or designee, whichever is longer. The investigator (or head of the study site in Japan) must contact BMS prior to destroying any records associated with the study.

BMS or designee will notify the investigator (or head of the study site in Japan) when the study records are no longer needed.

If the investigator withdraws from the study (eg, relocation, retirement), the records shall be transferred to a mutually agreed upon designee (eg, another investigator, study site, IRB). Notice of such transfer will be given in writing to BMS or designee.

RETURN OF STUDY TREATMENT

For this study, study treatments (those supplied by BMS, a vendor, or sourced by the investigator) such as partially used study treatment containers, vials, and syringes may be destroyed on site (as applicable; some sites will return unused study treatments depending on circumstances).

| If | Then |
|---|---|
| Study treatments supplied by BMS (including its vendors) | Any unused study treatments supplied by BMS can only be destroyed after being inspected and reconciled by the responsible Study Monitor unless study treatments containers must be immediately destroyed as required for safety, or to meet local regulations (eg, cytotoxics or biologics). If study treatments will be returned, the return will be arranged by the responsible Study Monitor. |
